2.0	22FEB2022	Updated	Updates according to protocol Amendments 1-5.
3.0	2MARCH2022	Updated	Updated the preliminary analysis set for safety and efficacy and added details of the interim analysis plan
4.0	26JULY2022	Update primary efficacy model and LOCF approach	Account dapagliflozin add-on in Week 12-24
5.0	12AUG2022	Cancel update on primary efficacy model, update the hyperlinks in Ver. 4.0	Collinearity issue in model update
6.0	28JUN2023	Update document for final analysis	Update the secondary analysis and remove LOCF approach.

List of Abbreviations

Abbreviation or Specialized Term	Definition
ACEi	angiotensin converting enzyme inhibitors
ADA	anti-drug antibody/antibodies
AE	adverse event
ALT	alanine aminotransferase
ANCOVA	analysis of covariance
ARB	angiotensin receptor blockers
AST	aspartate aminotransferase
ATC	anatomical therapeutic chemical class
BMI	body mass index
CSP	clinical study protocol
DKD	diabetic kidney disease
ECG	electrocardiogram
eGFR	estimated glomerular filtration rate
IPD	important protocol deviations
IXRS	interactive voice/web response system
LOCF	last-observation-carried-forward
MedDRA	Medical Dictionary for Regulatory Activities
PD	pharmacodynamic
PK	pharmacokinetics
PT	preferred term
SAE	serious adverse event
SGLT2i	sodium-glucose cotransporter-2 inhibitor(s)
SID	subject identification
SOC	system organ class
SPP	statistical programming plan
TEAE	treatment-emergent adverse event
T2DM	Type 2 diabetes mellitus
UACR	urine albumin : creatinine ratio
ULN	upper limit of reference range
WHO-DD	World Health Organization Drug Dictionary enhanced

1 INTRODUCTION

This document describes the statistical analysis methodology for protocol D9183C00001 Amendment 5 (14FEB2022). This document details the statistical summaries and analyses relating to each study objective and describes the general conventions and definitions that will be used. In addition, a set of table templates and specifications will be included in a statistical programming plan (SPP) to complement this document.

This study, D9183C00001 (FRONTIER 1), is a Phase 2b, randomized, double-blind, placebo-controlled, multi-centre study to evaluate the efficacy, safety, PK, and immunogenicity of MEDI3506 (Tozorakimab) in adult subjects with diabetic kidney disease (DKD); defined as subjects with T2DM and an eGFR of 25-75 mL/min/1.73 m² with a urine albumin : creatinine ratio (UACR) in the range of 100-3000 mg/g, who meet all eligibility criteria.

The study will investigate if MEDI3506 can reduce UACR in participants on standard of care without and with dapagliflozin. The dose-response relationship, and the safety and pharmacokinetic (PK) profile of MEDI3506 will be evaluated.

The study was started in November 2019 as a Phase 2a study and it was paused due to COVID-19 pandemic by March 2020. It was resumed in July 2020, and then endured several amendments where additional doses of MEDI3506 and the add-on of Dapagliflozin in the second half of the 6-month treatment period are introduced. Therefore, the study consists of two periods, where Period 1 is without Dapagliflozin and Period 2 is with Dapagliflozin. Accordingly, several cohorts of participants can be defined upon the evolution of the trial design as illustrated in [Table 1](#). Cohort 1 which are divided in two groups a and b, are subjects who have started on the Phase 2a. Cohort 1a participants were discontinued and did not have the opportunity to complete 6-month treatment due to COVID-19 pandemic. Participants in Cohort 1b were enrolled after the study was re-started and had the opportunity to complete 6-month treatment. These subjects will continue on treatment with MEDI3506/placebo without dapagliflozin. About 24 participants were randomized in Cohort 1 and 19 of them were discontinued when the study was paused. Cohort 2 are subjects who have started on the Phase 2a study but have not completed 12 weeks of treatment prior to Amendment 2. They were transitioned to the Phase 2b study and given dapagliflozin starting on Day 85 (Week 12). Finally, Cohort 3 are subjects who will enrol in ongoing Phase 2b study.

Table 1: Cohort of study participant by randomization scheme and active treatment regiment

Cohort	Randomization Scheme 1 (R1)	Randomization Scheme 2 (R2)	Active Treatment Regiment	
			6-month MEDI3506 monotherapy	MEDI3506 mono in 1 st 3 mons, MEDI3506 + Dapa in 2 nd 3 mons.
1a*	X		X	
1b*	X		X	
2	X			X
3		X		X

R1 = Randomization scheme for MEDI3506 60 mg, 300 mg, and matching placebo; R2 = Randomization scheme for MEDI3506 30 mg, 60 mg, 120 mg, 300 mg, and matching placebo.

* Participants in Cohort 1a were discontinued and did not have the opportunity to complete 6-month treatment due to COVID-19 pandemic. Participants in Cohort 1b were enrolled after the study was re-started and had the opportunity to complete 6-month treatment.

Should be noted that the method and the analysis details described in this document will be considered for Cohort 2 and 3. Cohort 1 will be summarized separately with some descriptive summary statistics and listing.

2 STUDY OVERVIEW

2.1 Study Objectives

2.1.1 Primary Study Objective(s)

To evaluate the effect of MEDI3506 as measured by change from baseline in urine albumin:creatinine ratio (UACR) at Week 24, when compared to placebo.

2.1.2 Secondary Study Objectives

- 1) To evaluate the effect of MEDI3506 as measured by change from baseline in urine albumin:creatinine ratio (UACR) at Week 12, when compared to placebo.
- 2) To evaluate safety and tolerability of MEDI3506 between Period 1 and 2 in subjects with DKD
- 3) To describe the PK and immunogenicity of MEDI3506 in subjects with DKD
- 4) To evaluate the effect of MEDI3506 in combination with ACEi or ARB between Period 1 and 2 on albuminuria in subjects with DKD

2.1.3 Exploratory Study Objectives

[figure not shown]
2.2 Study Design

This is a Phase 2b, randomized, double-blind, placebo-controlled, multi-center study to evaluate the efficacy, safety, PK, and immunogenicity of MEDI3506 in adult subjects with DKD. Approximately 565 subjects from around 130 study sites among multiple countries will be randomized (95:95:95:140:140) to MEDI3506 30, 60, 120, or 300 mg, or volume-matched placebo dosed subcutaneously (SC) every  days over a 168-day (24-week) treatment period.

Assuming 10% dropout, this will allow approximately 505 evaluable subjects to complete the study. The study includes a screening period of up to 35 days (Day -37 to Day -3), a 168-day (24-week) treatment period, and a 70-day (10-week) follow-up period. The study periods are shown in Figure 1.

Figure 1: Study Flow Diagram

2.3 Treatment Assignment and Blinding

An IXRS will be used for randomization to a treatment group and assignment of blinded investigational product kit numbers. A subject is considered randomized into the study when the investigator notifies the IXRS that the subject meets eligibility criteria and the IXRS provides the assignment of blinded investigational product kit numbers to the subject.

Subjects will be stratified at the time of randomization in order to ensure approximate balance between treatment groups within each sub-population.

- Stratum 1: Subjects without SGLT2i background outside Japan
- Stratum 2: Subjects with SGLT2i background outside Japan
- Stratum 3: Subjects without SGLT2i background in Japan
- Stratum 4: Subjects with SGLT2i background in Japan

Subjects will be randomized to receive 30, 60, 120, or 300 mg MEDI3506 (95, 95, 95, and 140 subjects, respectively) or 0.2 mL, 0.4 mL, 0.8 mL, or 2 mL placebo (32, 32, 32, and 44 subjects, respectively) by an IXRS system.

IXRS will also allocate 2 bottles of dapagliflozin (35 tablets each) at Visit 6 and 1 bottle of dapagliflozin (35 tablets) at Visit 8 to eligible subjects that will be used to cover the need of daily administration between two visits of MEDI3506/placebo administration. This will

ensure that the patient has sufficient stock of dapagliflozin if a visit is delayed. If there is any issue with one of the bottles (e.g. lost or damaged), the patient can receive a replacement at any visit (Visit 7 or Visit 8); kit replacement option is available in IXRS.

The procedure for using IXRS is as follows:

- The investigator or designee contacts the IXRS and provides the SID number and subject's baseline characteristic(s) used to verify that it is the same subject
- The correct number of kits of MEDI3506 and/or placebo will be assigned to the subject
- Confirmation of kit assignment is sent to the unblinded investigational product manager who prepares the investigational product to be dispensed to the subject per the response system and records the appropriate information in the investigational product accountability log
- Blinded study personnel will receive a notification containing a dose tracking number, that will not disclose how many kits are assigned to the subject.

Since MEDI3506 and placebo are not identical in appearance or viscosity, investigational product will be administered by site personnel who will not be directly involved in the management of study subjects. In the event that the treatment allocation for a subject becomes known to the investigator or other study staff involved in the management of study subjects, AstraZeneca must be notified immediately. If the treatment allocation for a subject need to be known to treat an individual subject for an adverse event (AE), the investigator must notify AstraZeneca immediately. The site will maintain a written plan detailing which staff members are blinded/unblinded and the process of investigational product preparation and administration used to maintain the blind.

2.4 Sample Size

A sample size of 565 subjects randomized using a 95:95:95:140:140 ratio to receive either 30, 60 mg, 120 mg, or 300 mg MEDI3506 or placebo will give approximately 85:85:85:125:125 evaluable subjects per group, assuming 10% dropout. This will provide at least 85% power for the 300 mg arm and 80% power for the 30, 60, and 120 mg arms to detect a 30% reduction in change from baseline to Day 169 (Week 24) in UACR between each MEDI3506 treatment group and placebo group (or placebo/ MEDI3506 ratio of 1.429) with a one-sided alpha of 0.05 without multiplicity adjustment, assuming a coefficient of variation of 1.31 or standard deviation of 1.0 in log scale.

3 STATISTICAL METHODS

3.1 General Considerations

3.1.1 Data Presentation

Data will be presented in data listings sorted by treatment group, subject number and date collected, where appropriate. Tabular summaries will be presented for each treatment with the placebo groups for volume matching combined. Categorical data will be summarized by treatment group with the number and percentage of subjects within each category.

Continuous variables will be summarized by treatment group with descriptive statistics including mean, standard deviation, median, minimum, and maximum. Baseline values will be defined as the last valid assessment prior to the first administration of investigational product unless otherwise specified.

All statistical tests will be 2-sided at an $\alpha = 0.10$ significance level unless stated otherwise. There will be no adjustment for multiplicity.

Data analyses will be performed using SAS[®] version 9.4 or higher (SAS Institute Inc., Cary, NC). The analytical results generated from SAS programs will follow AstraZeneca/MedImmune SAS programming standards and will be validated according to AstraZeneca/MedImmune SAS validation procedures.

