3.6 Safety Analyses

The analyses of the safety endpoints will be performed using the Safety Analysis Population for data cut-off at day 85 and all data available beyond day 85. The evaluations will be descriptive in nature, and observed differences will be evaluated for medical relevance. No formal statistical comparisons will be performed for the safety summaries.

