3.6.1 Adverse Events and Serious Adverse Events

Adverse events will be coded with MedDRA version 22.0 or later. Analysis of adverse events will include the type, incidence, severity and relationship to study investigational product summarized by MedDRA System Organ Class (SOC) and Preferred Term (PT), by treatment group as well as MEDI3506 overall. Treatment emergent adverse event is defined as any AE reported after the first IP up to the wash-out of MEDI3506 (5 half-lives: 90 days after the last dose of IP). If an AE is reported the day of the first IP (ie. Day 1) with a missing time, this AE will be considered as treatment emergent. The AEs summaries will include only treatment-emergent AEs (TEAE), i.e., those starting after the first administration of double-blind investigational product. Subjects will be counted once for specific PT or MedDRA SOC when calculating incidence rates. If the same AE Preferred Term occurs multiple times within a subject, the highest severity and level of relationship observed will be reported. Non-treatment-emergent AEs/serious adverse events (SAEs), i.e., those AEs with onset after screening but before the start of double-blind treatment will be presented in the listings. All TEAEs related to dapagliflozin will also be summarized. For subjects testing positive for COVID-19, overall summary of AEs, AEs by PT and SOC, summary of SAEs, AESI and the proportion of asymptomatic subjects will be provided.

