3.6.2 Adverse Events of Special Interest

The following AESIs have been defined in the study protocol and will be particularly monitored in this study:

- Serious hypersensitivity, including Type 1 to 4 hypersensitivity reactions, for example, anaphylaxis and severe allergic reactions, and immune complex disease.
- Injection-site reactions.
- Progression of heart failure.
- Serious infections, including opportunistic infections.
- Gastrointestinal adverse reactions.

In addition, Malignancy and COVID-19 disease may also be of interests.

All Treatment-emergent AESIs will be summarized by Special Interest Group and Preferred Term. Programmatic MedDRA search will be done in addition to AESI collected by CRF to ensure a thorough review.

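### The SAP's placebo pooling rule makes no exception for injection-site reactions, so the dose-by-dose comparison would mix any effect of injected volume with the effect of the drug

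*SAP*

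**What the plan says.** Section 2.2 describes the control as "or volume-matched placebo dosed subcutaneously (SC"). Section 2.3 gives the numbers. For the active arms: "Subjects will be randomized to receive 30, 60, 120, or 300 mg MEDI3506 (95, 95, 95, and 140 subjects, respectively"). For placebo: "0.2 mL, 0.4 mL, 0.8 mL, or 2 mL placebo (32, 32, 32, and 44 subjects, respectively").

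Section 3.1.1 then sets the general table convention: "Tabular summaries will be presented for each treatment with the placebo groups for volume matching combined". It states no exception.

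The safety sections do not bring the volume groups back. Section 3.6.1 tabulates adverse events "by treatment group as well as MEDI3506 overall". Section 3.6.2 lists "Injection-site reactions" among the adverse events of special interest and says: "All Treatment-emergent AESIs will be summarized by Special Interest Group and Preferred Term". Section 3.6 adds: "No formal statistical comparisons will be performed for the safety summaries". It also says that observed differences will be judged for medical relevance.

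**The concern.** Dose and volume rise together in the active arms, from 30 mg in 0.2 mL to 300 mg in 2 mL. The active arms alone therefore cannot show whether a rise in local reactions comes from the drug or from the volume injected. The placebo groups differ in volume and contain no drug, so they are the part of the design that can help to separate the two. The stated table rule merges them.

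For UACR the injected placebo volume has no evident bearing, and pooling is sensible. For injection-site reactions, volume may itself contribute to the event. If it does, pooled placebo is a comparator of smaller average volume than the 300 mg arm and of larger average volume than the low-dose arms. The errors run in opposite directions at the two ends of the dose range, which is a pattern that looks like a dose response. Section 1 names both dose-response and safety among the things to be evaluated, so the comparator shown in this table affects how local tolerability is read.

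**Working it through.** **Inputs from SAP section 2.3 (planned allocation).** Active: 95, 95, 95 and 140. Placebo: 32, 32, 32 and 44 at 0.2, 0.4, 0.8 and 2 mL.

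**The plan's own totals reproduce.** Placebo: 32 + 32 + 32 + 44 = 140. Trial: 3 × 95 + 140 + 140 = 565, as in sections 2.2 and 2.4.

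**Pairing of dose and volume.** Taken in the order listed: 30/0.2 = 60/0.4 = 120/0.8 = 300/2 = 150 mg/mL. The constant concentration supports reading 300 mg as the 2 mL arm.

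**Volume mix of pooled placebo.**
- 0.8 mL or less: 96/140 = 68.6%. At 2 mL: 44/140 = 31.4%.
- Mean volume: (32 × 0.2 + 32 × 0.4 + 32 × 0.8 + 44 × 2)/140 = 132.8/140 = 0.95 mL, against 2 mL in the 300 mg arm.

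**Size if the drug has no effect.** Let *a* be the reaction rate at 0.8 mL or less and *b* the rate at 2 mL. The SAP gives neither, so both are assumptions. Then:
- pooled placebo rate *p* = (96*a* + 44*b*)/140
- apparent risk ratio at 300 mg = *b*/*p*
- apparent risk ratio at each lower dose = *a*/*p*

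| *a* | *b* | *p* | 300 mg ratio | Lower-dose ratio | 300 mg excess (points) |
|---|---|---|---|---|---|
| 2% | 2% | 2.0% | 1.0 | 1.0 | 0 |
| 2% | 3% | 2.3% | 1.3 | 0.9 | 0.7 |
| 5% | 8% | 5.9% | 1.3 | 0.8 | 2.1 |
| 5% | 10% | 6.6% | 1.5 | 0.8 | 3.4 |
| 2% | 8% | 3.9% | 2.1 | 0.5 | 4.1 |

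Worked example, fifth row: *p* = (96 × 2% + 44 × 8%)/140 = 3.9%; 8/3.9 = 2.1; 2/3.9 = 0.5. Against matched placebo the expected ratio is 1.0 in every row.

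Over a wider grid (*b* from 5% to 30%, *a* of 2% or 5%), the spurious excess at 300 mg runs from 0 to 19 points. The ratio has a ceiling: as *a* approaches zero it tends to 140/44 = 3.2.

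**All doses combined.** The share of active subjects planned at 0.8 mL or less is 285/425 = 67.1%, against 68.6% for placebo. In the fifth row the combined active rate is (285 × 2% + 140 × 8%)/425 = 4.0%, against 3.9% on placebo. The combined MEDI3506 column is therefore nearly balanced for volume; the problem lies in the dose-by-dose columns.

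**What matched groups can show.** The comparisons would be 140 vs 44 at 300 mg and 95 vs 32 at each lower dose. At 8% in both groups, the 95% half-width for 300 mg is 1.96 × √[0.08 × 0.92 × (1/140 + 1/44)] = about 9 points. At 2%, a group of 32 has a chance of 0.98^32 = 52% of no event at all.

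**The case against.** The case for leaving the SAP alone has several parts.

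- **No contradiction.** The SAP states its pooling openly and applies it consistently, including to the primary analysis in section 3.4.1.2. This stands: the issue is a choice that fits one endpoint badly.
- **No volume effect is documented.** The SAP gives no reaction rates and does not say that volume causes reactions. This stands too, and it is why the range starts at no bias. But only a split by volume would show whether there is an effect.
- **Safety is descriptive.** No test is affected. Even at 2% and 8%, about 11 of 140 against 5 of 140 gives a Fisher p of about 0.20, and readers can see the volume design in section 2.3. Yet section 3.6 relies on judging observed differences, so the comparator on display still matters.
- **Matched groups are small and not a perfect control.** The low-dose comparisons will often be uninformative, and section 2.3 says that drug and placebo differ in viscosity. Matching on volume therefore does not isolate the active substance. Both points limit what the extra table can show, but they do not remove the mixing of volume and dose under the pooled rule.
- **Templates are elsewhere.** Section 1 places table templates in a separate programming plan, which is not shown and could contain a split. A reader might infer that every table will be pooled without exception. The SAP supports only that its stated rule has none. Section 3.1.1 also provides listings, but these are no substitute for a table with denominators.

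**Conclusion.** The point holds as a minor one. The stated rule combines placebo groups that the trial randomises by volume and makes no exception for the endpoint on which volume is most likely to matter. Its size depends wholly on an unknown: the false 300 mg risk ratio is 1.0 with no volume effect, 1.3 at 2% vs 3% and 2.1 at 2% vs 8%.

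Three stronger readings should be resisted:

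- A reader might infer that local tolerability will be misread, or that a twofold artefact is to be expected. The documents give no rates, so 2.1 is one assumed scenario, and the distortion is conditional on a volume effect.
- A reader might take 68.6% as the share actually treated. It is the planned allocation. The safety population includes Cohort 2, which section 1 places under a scheme with only 60 mg, 300 mg and matching placebo, so the actual mix may differ.
- A reader might conclude that pooling is wrong in general. Nothing here challenges it for UACR or for other safety tables, and no formal inference is affected.

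**What to change.** In sections 3.1.1 and 3.6.2, add one descriptive table of injection-site reactions, with counts, denominators and percentages. It should show each dose beside its volume-matched placebo group (by planned numbers, 95 vs 32 for 30, 60 and 120 mg, and 140 vs 44 for 300 mg) and also beside pooled placebo. Keep pooling for efficacy and for all other safety tables. Specify the table before unblinding.

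No volume-stratified risk difference is needed. It would add a comparative estimate to summaries that section 3.6 keeps descriptive, and the combined-dose comparison is already close to balanced for volume.

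The cost is one table from data already collected. Its limits belong in a footnote: the matched groups are small, low-dose placebo groups may have no events, and drug and placebo still differ in viscosity.

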3.1.2 Visit Windows

For statistical summaries and analyses by visits, the visits will be mapped based on the actual study days from the first IP dosing date according to the protocol (section 4.2 Table 5 and Table 6) and labelled as Baseline, Day 15, Day 29, Day 57, Day 85, Day 113, Day 141, Day 169, Day 200, and Day 230.

Baseline values will be defined as the last assessment prior to the first administration of study medication (Day 1).

Except the off-treatment visits of the early dropouts (any visit up to including EOT), the visit windows for post-baseline visits will be mapped based on following the table. Any out of window visit will be labelled as unscheduled visit.

Visit (nominal study day)	Visit Window (actual study day)
Baseline ^a	1
Day 15	9-21
Day 29	22-43
Day 57	44-71
Day 85	72-99
Day 113	100-127
Day 141	128-155
Day 169	156-185
Day 200/Follow up	186-215

Visit (nominal study day)	Visit Window (actual study day)
Day 230/Follow up	216-end of study

^aLast assessment prior to first administration of study medication

- If multiple valid assessments fall within the same visit window, the following rules will be applied.
 - If there are two or more valid observations within the same visit window, then the one closest to the scheduled visit will be used in the analysis.
 - If two valid observations are equidistant from the scheduled visit, then the one with the earlier collection date will be used in the analysis.
 - If two valid post-baseline valid observations are collected on the same day, then the one with the earlier collection time will be included in the analysis.
- **For subjects who dropout treatment early**, the follow up visits (any visit after EOT) will be mapped as follows:
 - Determine the last dose visit window based on its actual study day as per the above table. If the last dose was taken up to actual study day 21, then the last dose visit window will be considered as Unscheduled.
 - Any measurement within (\leq) 2 weeks post last dose will be aligned with the last dose visit window.
 - Any measurement beyond ($>$) 2 weeks but within (\leq) 6 weeks post last dose will be aligned with the next protocol scheduled visit window after the last dose visit window. Note: if the last dose visit window is Unscheduled, then the next protocol scheduled visit window should be considered as Day 29.
 - Any measurement beyond ($>$) 6 weeks but within (\leq) 10 weeks post last dose will be mapped as Day 200/Follow up.
 - Any measurement beyond ($>$) 10 weeks post last dose will be mapped as Day 230/Follow up.

